##### [11] Laboratory tests (peripheral leukocyte count, peripheral lymphocyte count, $\beta$ -D-glucan)

2) Survey form

(1) Patient characteristics prior to and at the start of treatment

The following will be recorded for both treatment groups.

[1] Height/weight

[2] Inpatient/outpatient status

Indication (Patients with rheumatoid arthritis), stage and grade (Steinbrocker stage), and functional class (Steinbrocker functional class)

[3] Duration of disease

[4] Clinical history (past history and concurrent illness)

[5] History of smoking (history of smoking at treatment start)

[6] Family history of malignant tumor

(2) Previous treatment drugs for rheumatoid arthritis (3 months before treatment start)

The following will be recorded for both treatment groups.

[1] MTX

- Past use (presence/absence)
- Weekly dosage
- Duration of treatment

[2] Oral steroid use for rheumatoid arthritis

- Past use (presence/absence), period or treatment

[3] Tacrolimus

- Past use (presence/absence)
- Duration of treatment

(3) Dose record

[1] Xeljanz group

Number of doses per day, treatment period, reason for change (if there has been a change in administration)

[2] Control group

If there has been a switch to another type of pharmacotherapy, excluding Xeljanz, during the observation period, the case will be handled as a continued surveillance case, and the treatment record should be continuously entered.

In cases where Xeljanz has been administered, surveillance as a member of the control group will be handled as discontinued, and registration in the Xeljanz group will be necessary.

● MTX

Name of drug (name of product), weekly dosage, and duration of treatment

● Pharmacotherapy with drugs other than MTX (biological preparation, DMARDs, immunosuppressants, oral steroid preparations)

Name of drug (name of product), daily dosage (oral steroids), and duration of treatment

(4) Concomitant therapy (Xeljanz group)

For drug therapy, covering the period starting 3 months prior to the start of treatment in this Surveillance

and ending at the completion or discontinuation of the observation period will be completed. Medications used for the treatment of adverse events should also be recorded.

[Concomitant therapies coadministered with Xeljanz]

- [1] MTX
- [2] Biological preparations\*
- [3] DMARDs other than MTX and immunosuppressants\*
- [4] Oral steroid
- [5] Other drugs

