### 6.3. Covariates

For both the Xeljanz and control groups, candidate covariates related to the development of malignant tumors and serious infections are shown below.

Covariates	Malignant tumor	Serious infection
Sex	○	○
Age	○	○
Weight	○	○
Stage of rheumatoid arthritis	○	○
Class of rheumatoid arthritis	○	○
Duration or disease	○	○
Past history (infection)	×	○
Past history (malignant tumor)	○	×
Past history (lung disorder)	×	○
Past history (interstitial pneumonia)	×	○
Complication (infection)	×	○
Complication (malignant tumor)	○	×
Complication (hepatitis B)	○	×
Complication (hepatitis C)	○	×
Complication (diabetes mellitus)	×	○
Smoking history	○	○
Family history of malignant tumors (including lymphoma)	○	○
History of MTX use (Within 3 months prior to the start of survey)	○	○
MTX criteria	○	○
History of oral steroid use (Within 3 months prior to the start of survey)	○	○
History of tacrolimus use (Within 3 months prior to the start of survey)	○	○
Past use of biological agents (Within 3 months prior to the start of survey)	○	○

Covariats	Malignant tumor	Serious infection
Initial dose of Xeljanz	○	○
Neutrophil count	○	○
Lymphocyte count	○	○
Prophylactic administration to prevent tuberculosis	×	○
Prophylactic administration to prevent pneumocystis jiroveci pneumonia	×	○
Prophylactic administration to prevent hepatitis B	×	○
DAS28	○	○

○: Applicable, ×: Not applicable

Covariates may be added or removed based on the results of the interim analyses of this survey and newly obtained findings. In that case, this plan will be revised.

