**Table 3. Categories of Tabulation Items for the Status of the Implementation of Tests**

Item	Category
Test	Test (implemented if at least one is met), chest X-ray or chest CT (chest X-ray, chest CT), interferon $\gamma$ or tuberculin reaction (interferon $\gamma$ , tuberculin reaction), hepatitis B and C virus test (HBs antigen, HBs antibody, HBc antibody, HBV-DNA test, HCV antibody)
Test timing	after the initiation of administration of Xeljanz (Day 2-), before the initiation of administration of Xeljanz $\leq$ 3 months (Day -30 to Day 0), before the initiation of administration of Xeljanz $>$ 3 months (-Day 31), before the initiation of administration of Xeljanz $>$ 3 months to $\leq$ 6 months (Day -183 to Day -31), before the initiation of administration of Xeljanz $>$ 6 months to $\leq$ 12 months (Day -364 to Day -182), before the initiation of administration of Xeljanz $>$ 12 months to $\leq$ 24 months (Day -729 to Day -365), before the initiation of administration of Xeljanz $>$ 24 months (-Day -730)

- Past medical histories**

In the safety analysis set, the number and proportion of patients with past medical histories will be calculated for each system organ class (SOC) and preferred term (PT).

- Complications**

In the safety analysis set, the number and proportion of patients with complications (current medical history) will be calculated for each SOC and PT.

- Concomitant drugs**

In the safety and efficacy analysis sets in the Xeljanz group, the number and proportion of patients who used concomitant drugs will be calculated. A biological therapeutic or immunosuppressant terminated on the same day as the first dose of Xeljanz or started on the same day as the last dose of Xeljanz will not be considered as a concomitant drug.

Similarly, the number and the proportion of patients will be calculated by methotrexate (MTX), biological agents, DMARDs and immunosuppressive agents other than MTX, oral steroids and other drugs.

- Non-drug therapies**

In the safety and efficacy analysis sets in the Xeljanz group, the number and proportion of patients who underwent surgical therapies for rheumatoid arthritis (surgery scheduled before the initiation of this survey) will be calculated.

- **Prior medications**

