Past history (hepatitis C)	Absent, Present	
Past history (other hepatitis)	Absent, Present	
Past history (hepatitis B virus carrier)	Absent, Present	
Past history (hepatitis C virus carrier)	Absent, Present	
Past history (other hepatitis virus carrier)	Absent, Present	
Past history (renal dysfunction)	Absent, Present	
Past history (metabolic abnormality)	Absent, Present	
Past history (diabetes mellitus)	Absent, Present	

Item	Category	Note
Past history (lipid abnormality)	Absent, Present	
Past history (anemia)	Absent, Present	
Past history (others)	Absent, Present	
Complication	Absent, Present	
Complication (infection)	Absent, Present	
Complication (herpes zoster)	Absent, Present	
Complication (tuberculosis-related disease)	Absent, Present	
Complication (malignant tumor)	Absent, Present	
Complication (autoimmune disease)	Absent, Present	
Complication (Sjogren's syndrome)	Absent, Present	
Complication (cardiovascular disease)	Absent, Present	
Complication (hypertension)	Absent, Present	
Complication (angina pectoris)	Absent, Present	
Complication (myocardial infarction)	Absent, Present	
Complication (heart failure)	Absent, Present	
Complication (arrhythmia)	Absent, Present	
Complication (pulmonary disorder)	Absent, Present	
Complication (interstitial pneumonia)	Absent, Present	
Complication (gastrointestinal disorder)	Absent, Present	
Complication (diverticulum)	Absent, Present	
Complication (gastrointestinal perforation)	Absent, Present	

Item	Category	Note
Complication (hepatic dysfunction)	Absent, Present	
Complication (hepatitis B)	Absent, Present	
Complication (hepatitis C)	Absent, Present	
Complication (other hepatitis)	Absent, Present	
Complication (hepatitis B virus carrier)	Absent, Present	
Complication (hepatitis C virus carrier)	Absent, Present	
Complication (other hepatitis virus carrier)	Absent, Present	
Complication (renal dysfunction)	Absent, Present	
Complication (metabolic abnormality)	Absent, Present	
Complication (diabetes mellitus)	Absent, Present	
Complication (lipid abnormality)	Absent, Present	
Complication (anemia)	Absent, Present	
Complication (others)	Absent, Present	
Smoking history 1	Absent, Present, Unknown	
Smoking history 2	Past history absent, Past history present, Present, Unknown	
Family history of malignant tumors (including lymphoma)	Absent, Present, Unknown	
History of MTX use (Within 3 months prior to the start of survey)	Absent, Present, (History) Unknown	

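### The serious-infection adjustment set includes past but not current lung disorder and interstitial pneumonia, although the current items are collected in both groups

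*SAP*

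**What the plan says.** The covariate table in SAP 6.3 marks two lung items for serious infection, both past history: "Past history (lung disorder" and "Past history (interstitial pneumonia". The only current illnesses marked in that column are "Complication (infection" and "Complication (diabetes mellitus".

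The SAP keeps past and current illness apart. Section 8.2.2 tabulates past medical histories under one bullet and, under another, "patients with complications (current medical history) will be calculated for each SOC and PT". Appendix 11.1.2 has separate absent/present items for the current conditions, "Complication (pulmonary disorder" and "Complication (interstitial pneumonia", alongside their past-history counterparts. Neither is restricted to the Xeljanz group, whereas items such as blood pressure and hepatitis serology are.

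Protocol 7.1, under the survey-form patient characteristics recorded for both groups, lists "Clinical history (past history and concurrent illness".

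**The concern.** Comparing serious infections with the control group is a stated objective (Protocol 1; SAP 2.2). Treatment is not randomised, so the comparison depends on the adjustment set. By selecting past lung disease as a covariate for this outcome, the plan accepts that lung disease is relevant to it. Lung disease present at the start of treatment could plausibly influence both the choice of antirheumatic drug and the risk of a serious infection, yet the list has no term for it.

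If current lung disease is unevenly distributed between the groups, part of that difference can pass into the hazard ratio and be read as a drug effect. The direction is unknown, because the documents do not say how lung disease steers prescribing.

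**Working it through.** **Which lung items are used where**

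| Item | SAP 6.3, serious infection | Appendix 11.1.2 | Appendix 11.1.3 (safety factors, Xeljanz group) |
|---|---|---|---|
| Lung (pulmonary) disorder, past | Yes | Yes | Yes |
| Interstitial pneumonia, past | Yes | Yes | Yes |
| Pulmonary disorder, current | No | Yes | Yes |
| Interstitial pneumonia, current | No | Yes | Yes |

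Through SAP 5.4 and the subgroup analysis in 8.2.3.2, serious infections among Xeljanz patients are tabulated and tested by the current lung items. The plan therefore studies them within one group but does not adjust for them between groups.

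**Where the 6.3 list goes**

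1. It supplies the explanatory variables of the propensity score (8.1.6), and hence the weights.
2. It supplies the adjustment terms of the Cox model and the factors for the pooled incidence ratios and differences (8.2.3.1.2).
3. The balance output in 8.2.3.1.2 covers only the background items used as covariates. The background tables in 8.2.2 may show crude frequencies of current lung disease, but they do not show balance after weighting.
4. Multiple imputation does not help. For a patient recorded as current only, the past-history value is a valid absent, not a missing value.

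**Size**

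The plan gives no figure to reproduce on this point. All inputs below are assumptions: prevalence of current lung disease p1 (Xeljanz) and p0 (control) between 5% and 15%, and a hazard ratio HR of 2 to 3 for serious infection given current lung disease. The usual factor for one omitted binary confounder is

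F = [1 + p1(HR − 1)] / [1 + p0(HR − 1)]

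| p1 vs p0 | HR = 2 | HR = 3 |
|---|---|---|
| 5% vs 5% | 1.05/1.05 = 1.00 | 1.10/1.10 = 1.00 |
| 10% vs 5% | 1.10/1.05 = 1.05 | 1.20/1.10 = 1.09 |
| 15% vs 5% | 1.15/1.05 = 1.10 | 1.30/1.10 = 1.18 |
| 5% vs 10% | 1.05/1.10 = 0.95 | 1.10/1.20 = 0.92 |
| 5% vs 15% | 1.05/1.15 = 0.91 | 1.10/1.30 = 0.85 |

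With a weaker association, HR = 1.5, 15% vs 5% gives 1.075/1.025 = 1.05. Equal prevalence gives 1.00 whatever the hazard ratio.

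**The case against.** **The list has a pattern.** A reader might infer that leaving out the current lung items is arbitrary, because the malignancy column carries both past and current malignant tumor. The table does not support that. In each column only the outcome's own condition is paired: malignant tumor for malignancy, infection for serious infection. Every other illness appears once: hepatitis B, hepatitis C and diabetes as current, the two lung items as past. What stands is narrower: for these two items the past version was chosen and the current one left out.

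**The form is not shown.** A reader might infer that every patient with active lung disease is coded as having none. The documents do not establish this. They do not say that past and current boxes exclude each other, or how a continuing illness is ticked. A patient with both recorded is captured by the past-history term. The point applies to patients recorded as current only.

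**Related covariates are already in the model.** Past lung disease, age, smoking, oral steroids, disease stage and class, and pneumocystis prophylaxis are adjusted. To the extent that they track current lung disease, the factors above overstate what remains.

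**Status of the analysis.** SAP 4 calls the tests exploratory, 6.3 calls the covariates candidates, and text following 8.2.3.1.3 is redacted, so a further adjusted analysis may exist there. None of this changes the 6.3 list, which can be altered only by revising the plan.

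**Timing.** SAP version 10.0 was written after database release. A change to the main models now would be post hoc. That objection stands, and the remedy allows for it.

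**Conclusion.** The gap is real and worth correcting. Patients recorded with current lung disease only are adjusted as if they had none, in a comparison that relies on adjustment, and the planned balance output would not reveal it.

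The size rests wholly on assumed inputs: a factor of 1.00 to 1.18, or 0.85 to 1.00 with the imbalance reversed, read as outer limits for those inputs. No bias at all is within the range, so the documents do not show that the result will be distorted.

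Two further readings are not supported:

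- A reader might infer that current lung disease is a stronger marker of risk than past disease. That is clinical judgement; no passage states it.
- A reader might extend the point to current renal and hepatic dysfunction, which are also missing from the 6.3 table. The version 8.0 revision entry says both were added to 6.3, and no later entry records their removal. Their absence may come from how the table was read from the PDF, so it is not part of this point.

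**What to change.** In SAP 6.3, add "Complication (pulmonary disorder" and "Complication (interstitial pneumonia" to the serious-infection column. Alternatively, replace the two past-history rows with one three-level variable per condition: none, past only, current. State how a patient with both past and current recorded is coded. Carry the items into the propensity score, the Cox model, the pooled estimates and the balance output.

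If the main models are already locked, leave them unchanged and report the extended adjustment as a labelled sensitivity analysis, with the weighted and unweighted frequency of current lung disease by group.

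The cost is a SAP revision, a program change and two more binary covariates (or two three-level ones). No new data collection is needed. The drawback is a late change to a covariate list that has already been revised several times, and this should be disclosed.

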## 7 Survey items and schedule

This Surveillance should be conducted in accordance with the following observation schedule.

Survey item	Observation period	Subject	Registration form	Survey form								
				Booklet 1 *6				Booklet 2	Booklet 3	Booklet 4		
				Pre-dose*1 During treatment*2	Start of surveillance	Month 1	Month 3	Month 6	Month 12	Month 24	Month 36	
Registration form	Confirmation of target patients, prior treatment of MTX, drugs to be investigated, ID number, patient's initials, gender, date of birth or age at the start of treatment, and start date of treatment (or surveillance)	Xeljanz group Control group	Xeljanz group	●	-	-	-	-	-	-	-	
	Contraindication, tuberculosis check, hepatitis B virus test, and clinical laboratory	Xeljanz group		●	-	-	-	-	-	-	-	
Survey Form	Patient characteristics	Both groups	Xeljanz group	-	●	-	-	-	-	-	-	
	Dose record	Both groups		-	↔							
	Concomitant therapy (Pharmacotherapy)	Xeljanz group		-	↔							
	Pneumococcus vaccination*3	Both groups		-	↔							
	Prophylactic administration*4	Both groups		-	↔							
	Chest X-rays or CT	Xeljanz group		-	●	↔		●	●	●	●	
	Tuberculosis check	Xeljanz group		-	●	-	-	-	-	-	-	
	Hepatitis B/C virus test	Xeljanz group		-	●							
	Blood pressures (systolic/diastolic)	Xeljanz group		-	●	-	-	●	●	●	●	
	Clinical laboratory	Xeljanz group		-	●	●	●	●	●	●	●	
	Tender/swollen joint count, patient/doctor-reported outcome, CRP, and ESR	Xeljanz group		-	●	-	-	●	●	●	●	
	Adverse events*5	Xeljanz group		-	↔							
		Control group		-	Serious infection			↔				
	Tests/examinations related to adverse events	Xeljanz group		-	↔							
Follow	Follow-u*6	Both groups		-	Periodically performed for 3 years from the start of treatment for subjects who prematurely discontinue treatment*6							

●: Essential data

\*1: Patients in the Xeljanz group should be registered in principle no later than 1 week prior to the start of treatment.

\*2: Patients in the control group should be registered in principle no later than 2 weeks after the start of surveillance.

\*3: Information on patients in the control group should be collected until 12 months after the start of surveillance.

\*4: Prophylactic administration to prevent tuberculosis, pneumocystis jiroveci pneumonia, and hepatitis B (nucleic acid analogs)

Information on patients in the control group should be collected until 12 months after the start of surveillance.

- Treatment start to Month 6: Malignant tumor and serious infection

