##### [2] Drugs to be investigated

- Xeljanz group: Patient category :Newly prescribed, transferred from clinical study, or prescribed at other medical facility (name of the medical facility)

Control group: Pharmacotherapy: whether or not MTX has been administered, whether or not biological preparations have been administered, whether or not disease-modifying antirheumatic drugs (DMARDs) or immunosuppressants have been administered

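### Recent biologic use is an adjustment covariate for both groups, but the protocol gives no control-group item that captures it, so the between-group analyses cannot control for it

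*SAP*

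**What the plan says.** SAP 6.3 introduces its covariate table with "For both the Xeljanz and control groups, candidate covariates related to the development of malignant tumors and serious infections are shown below". The row "Past use of biological agents (Within 3 months prior to the start of survey" is marked as applicable to malignant tumor and to serious infection. SAP 11.1.2 gives the item two levels, Absent and Present, with no Unknown level and no note restricting it to the Xeljanz group. The 6.3 list feeds the pooled estimates, the adjusted Cox model, the propensity score and the balance table (SAP 8.1.6, 8.2.3.1.1 and 8.2.3.1.2).

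For missing covariates, SAP 7 and 8.1.6 prescribe multiple imputation in the group comparison, with unknown values treated as missing. Neither section says how this covariate is derived for controls.

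On data collection, Protocol 7.1 2) has a section for both groups headed "Previous treatment drugs for rheumatoid arthritis (3 months before treatment start", which asks for MTX, oral steroid and tacrolimus only. Biologics appear in a separate section headed "Concomitant therapy (Xeljanz group", whose window is described as "For drug therapy, covering the period starting 3 months prior to the start of treatment in this Surveillance". The schedule table in Protocol 7 likewise assigns the row "Concomitant therapy (Pharmacotherapy" to the Xeljanz group.

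**The concern.** A covariate can adjust a comparison only if it is measured in both groups. Here the plan adjusts for a factor that, on the protocol's text, is observed in one group. Comparing malignant tumors and serious infections with the control group is a stated objective (Protocol 1, SAP 2.2), and recent biologic exposure could plausibly affect both the choice of treatment and the risk. With the item on the covariate list and in the balance table, a reader would believe it had been controlled for. The adjusted ratio could instead carry the full confounding from this factor, or under one coding a new bias created by the adjustment itself.

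**Working it through.** **Step 1. Can any control-group record supply the item?**

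- Prior-treatment section, both groups (Protocol 7.1 2) (2)): 3-month window, but no biologic item.
- Concomitant-therapy section (Protocol 7.1 2) (4)): 3-month window and biologics, but Xeljanz group only.
- Registration form, drugs under investigation (Protocol 7.1 1) [2]): controls answer "whether or not biological preparations have been administered". There is no 3-month window and no stop date, and the item sits with the therapy under study, not with history.
- Control dose record (Protocol 7.1 2) (3)): covers "Pharmacotherapy with drugs other than MTX (biological preparation, DMARDs, immunosuppressants, oral steroid preparations" with duration, but states no pre-start look-back. SAP 11.1.1 also sets control Day 1 at the earliest start date in that record. No entry can then begin before Day 1; a pre-start biologic entered there would move Day 1 back to itself.

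None of the four yields biologic use in the 3 months before start for a control patient.

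**Step 2. What happens under each possible coding?**

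The plan states no figure that depends on this covariate, so there is none to reproduce. Let pX and pC be the true shares with recent biologic use in the Xeljanz and control groups, and HR its effect on the hazard. All three are assumed. Events are taken as rare, and the other covariates are set aside.

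*(a) All controls coded Absent, Cox or pooled estimate.* The Present stratum has no control events and no control person-time, so in the pooled incidence ratio of SAP 8.1.6 it adds zero to numerator and denominator. What remains compares biologic-free Xeljanz patients with all controls:

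estimated ratio = true ratio × 1/[1 + pC(HR−1)]

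- pC = 0.2, HR = 1.3: 1/1.06 = 0.943
- pC = 0.4, HR = 1.5: 1/1.20 = 0.833 (a true 1.2 becomes 1.2 × 0.833 = 1.00)
- pC = 0.6, HR = 2.0: 1/1.60 = 0.625

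*(b) All controls coded Absent, propensity weighting.* The SAP gives Xeljanz patients weight 1 and controls θ/(1−θ), where θ is the propensity score. With 4000 and 2000 patients and pX = 0.4, the Absent stratum has θ = 2400/(2400 + 2000), so every control has weight 2400/2000 = 1.2. A constant weight cancels. The Present Xeljanz patients stay in with no counterpart, so the ratio is the crude one:

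estimated ratio = true ratio × [1 + pX(HR−1)]/[1 + pC(HR−1)]

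*(c) All controls missing, then imputed.* The imputation can learn the item only from Xeljanz patients. Taking the imputed values as unrelated to the controls' own history, the factor is balanced by construction, adjustment does nothing, and the ratio is again the crude one in (b).

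Results for a true ratio of 1.00:

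| pX | pC | HR | (a) Cox or pooled, all Absent | (b), (c) weighted or imputed |
|---|---|---|---|---|
| 0.2 | 0.5 | 2.0 | 1/1.50 = 0.67 | 1.20/1.50 = 0.80 |
| 0.4 | 0.3 | 1.5 | 1/1.15 = 0.87 | 1.20/1.15 = 1.04 |
| 0.6 | 0.1 | 2.0 | 1/1.10 = 0.91 | 1.60/1.10 = 1.45 |

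Over pX 0.2–0.6, pC 0.1–0.5 and HR 1.2–2.0, (a) runs from 0.67 to 0.98, and (b) and (c) from 0.80 to 1.45. With HR = 1 there is no bias under any coding.

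**The case against.** A reader might infer that controls just off a biologic are counted as biologic-free and that Xeljanz is therefore made to look falsely safe. The documents do not support that as a general statement. No section sets an unrecorded value to Absent, and the written rule sends missing covariates to multiple imputation. The lack of an Unknown level is weak evidence, since oral steroid use within 3 months, tacrolimus use and all the medical-history items share it. Absent by default is plausible if the item is derived from drug-record dates, as the neighbouring oral-steroid item appears to be, but it remains an inference. The falsely safe direction holds only for the Cox and pooled estimates, only under all-Absent coding, and only for HR above 1.

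The other side can go further. The SAP uses a Xeljanz-only note freely elsewhere, so its absence here suggests the authors expected control data. Prior medications in SAP 8.2.2, which include biologics, are not restricted to the Xeljanz group. The registration question could be read as history, and the case report form is not among the documents. The planned single-factor tables and standardized differences would make a zero count of Present controls conspicuous. The list is one of candidates, the tests are exploratory (SAP 4), and text after the analysis of deaths is redacted and may hold sensitivity analyses.

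Much of this stands as a reason to check the source before deleting anything. It does not supply a source. The registration question has no window, and the prior-medication text in 8.2.2 defines its same-day rule by the first Xeljanz dose. Under imputation the balance table would look good precisely because the values were borrowed from the other group, so the diagnostics would not reveal the problem in that case.

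**Conclusion.** Wrong as written, and more than a missing detail. On the protocol's text, biologic use in the 3 months before start cannot be known for controls, and under either coding the pooled, Cox and weighted comparisons do not control for it. The balance table would show either a false contrast or an imputed balance.

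The size and direction are not established. They depend on an undocumented derivation and on pX, pC and HR, which the documents do not give and which may differ between malignant tumor and serious infection. The 0.83 factor describes one branch under assumed values. The weighted and imputed branches can err either way. The conclusion would change if the case report form or database holds pre-start biologic entries for controls.

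**What to change.** First check whether the control records hold biologic data for the 3 months before start.

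- If they do, state the source and derivation in SAP 6.3 and 11.1.2, and code controls without such coverage as missing, not Absent.
- If they do not, remove the item from everything used between groups: propensity score, imputation model, Cox model, pooled estimates and balance table. Keep it for Xeljanz-only analyses. State that recent biologic use is an unadjusted confounder, and add a bias analysis that varies pX, pC and HR in [1 + pX(HR−1)]/[1 + pC(HR−1)], separately for the two outcomes. The one-group form 1/[1 + pC(HR−1)] must not be used here: it describes the coding error, not the confounding that remains once the item is dropped.

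SAP 6.3 already allows covariates to be removed by revising the plan. The cost is SAP wording, a shorter covariate list and a rerun of any adjusted analyses already done; no new data collection is needed. The downside is that the sponsor must declare a known confounder as unadjusted.
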